#### 4.3.6.3. Supplementary analyses

Additional estimand is described by the following attributes:

- **Population:** Japanese female participants with acute uncomplicated cystitis with qualifying bacterial uropathogen(s) resistance to “two or more” specific classes of antimicrobials at Baseline
- **Treatment Condition:** Gepotidacin 1500 mg BID for 5 days vs Nitrofurantoin 100 mg BID for 5 days, regardless of adherence
- **Variable:** -Microbiological response at the TOC Visit
- **Summary Measure:** Proportion of participants achieving microbiological success in the gepotidacin arm
- **Handling of Intercurrent Event:**
  - Study treatment discontinuation (due to any reason) – treatment policy
  - Use of systemic antimicrobials prior to the visit of interest – composite strategy. This ICE is captured through the definitions of microbiological response (see Section 6.2.1.1)

The same BDB approach will be used as therapeutic response in MDR (Refer to Section 4.3.4.3).

#### 4.3.7. Investigator Assessment of Clinical Response at the TOC Visit

##### 4.3.7.1. Definition of Estimand

- **Population:** Japanese female participants with acute uncomplicated cystitis
- **Treatment Condition:** Gepotidacin 1500 mg BID for 5 days, regardless of adherence
- **Variable:** Investigator assessment of clinical response at the TOC Visit
- **Summary Measure:** Proportion of participants with investigator assessed clinical response of success, failure and indeterminate/missing on the gepotidacin arm
- **Handling of Intercurrent Event:**
  - Study treatment discontinuation (due to any reason) – treatment policy
  - Use of systemic antimicrobials on or prior to the visit of interest – composite strategy

#### 4.3.7.2. Main analytical approach

This analysis is based on ITT Population. Below are the categories of response and response.

Definition	Clinical Response
Sufficient resolution of acute cystitis signs and symptoms such that no additional systemic antimicrobial therapy is required for the current infection	Clinical Success
Participant met any one of the criteria below: 
 
• No apparent response to treatment (persistence or progression of any pretreatment clinical signs and symptoms)
 
• Use of additional systemic antibiotic(s) for the current infection
 
• Death related to acute cystitis prior to the visit
 
	Clinical Failure
Determination of clinical response could not be made at the visit for any of the following reasons: 
 
• Participant was lost to follow-up and/or the clinical assessment was not undertaken
 
• Use of confounding systemic antibiotic(s) for another infection
 
• Death prior to the visit where acute cystitis was clearly noncontributory
 
	Indeterminate

The missing data at TOC visit including outside the analysis window will be handled as shown in Section [6.2.1.5](#).

The number and proportion of participants with investigator assessed clinical response of success, failure and indeterminate/missing at the TOC Visit by treatment group based on ITT Population. Reasons for an assessment of failure and indeterminate responses will also be summarized.

The 95% Exact Clopper Pearson CI for the proportion of participants with success will be presented as a binomial proportion for each treatment group.

#### 4.3.8. Gepotidacin plasma and urine PK concentrations

##### 4.3.8.1. Definition of Estimand

- **Population:** Japanese female participants with acute uncomplicated cystitis
- **Treatment Condition:** Gepotidacin 1500 mg BID for 5 days, regardless of adherence
- **Variable:** Gepotidacin plasma and urine PK concentrations
- **Summary Measure:** Summary statistics (appropriate for each type of endpoint) in the gepotidacin arm
- **Handling of Intercurrent Event:**
  - Study treatment discontinuation (due to any reason) – while on treatment strategy (treatment phase defined as from first dose to On-therapy Visit)

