PK blood sample		X	X				
Sparse PK blood samples will be collected.
 
 At the Baseline Visit, the PK blood samples will be collected at 1-2 hours post-dose as peak concentration. At the On-therapy Visit, the PK blood samples will be collected at pre-dose as trough concentration (i.e., 12 hours post-dose, which is at the end of the dosing interval from the previous dose) and at 1-2 hours post-dose as peak concentration. 
(Further detailed information will be provided in the SRM.)

PK urine sample		X	X				
 At the Baseline Visit, samples will be collected from pre-dose to approximately 2 hours (1 to 3 hours) post-dose as pooled urine. At the On-therapy Visit, samples will be collected at pre-dose (i.e., 12 hours postdose as spot urine, which is at the end of the dosing interval from the previous dose) and from pre-dose to approximately 2 hours (1 to 3 hours) post-dose as pooled urine. 
(Further detailed information will be provided in the SRM.)

Study treatment							
Administer oral dose of study treatment		X	X				
 Participants will receive oral study treatment BID for 5 days under double-blind, double-dummy conditions. The first oral dose will be administered at the study site during the Baseline Visit; participants will self-administer as outpatients thereafter, beginning with the second dose, excluding the day of On-therapy Visit (i.e., taking morning dose at study site). Each dose should

Visit	Baseline		On-Therapy ^a	TOC ^b	Follow-up	Early Withdrawal	Notes
Study Day	1		2 to 4	10 to 13	28±3	NA	
be taken after food consumption and with water. The date and time of each dose administered at the study site will be recorded in the source documents.
 
 At the On-therapy Visit, whenever it is possible, the participant will have the pregnancy test performed at the study site. If the visit coincides with the 8th dose, the participant will take their next dose of study treatment at the study site after negative pregnancy test results are confirmed. Note: The On-therapy Visit should be scheduled to support completion of the postdose ECG within the protocol-defined window. Also, in a woman of childbearing potential, the high sensitivity pregnancy test must be performed and show negative results at the latest before Dose 8 of study treatment is taken.
Procedure	Pre-dose	Post-dose					

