4.3. Justification for Dose

The oral gepotidacin dose in this study is 1500 mg BID (total daily dose of 3000 mg) for 5 days. A 5-day dosing duration is in alignment with current treatment guidelines for efficacious antibacterial treatment of acute uncomplicated cystitis in women, which typically ranges from 3 to 7 days [Gupta, 2011b;; EAU, 2019; Yamamoto, 2017]. The safety and tolerability at this oral dose and duration have been evaluated in Phase I studies and in Phase II studies (BTZ116704 and 206899) (see IB for details).

Furthermore, high urine concentrations of gepotidacin are expected in this study based on a healthy volunteer Phase I study (BTZ117351) and a Phase IIa study in participants with acute uncomplicated cystitis (206899). In BTZ117351, approximately 287 mg of unchanged gepotidacin was excreted in urine after a single oral 1500-mg (2 × 750-mg tablets) dose of gepotidacin (minimum urine area under drug concentration-time curve over 12 hours [AUC_{12h}]=807 $\mu\text{g.h/mL}$). In the Phase IIa study, 206899, in participants with acute uncomplicated cystitis, approximately 460 mg of unchanged gepotidacin was excreted in urine over the steady-state dosing interval of 12 hours after repeat BID oral dosing of 1500 mg (2 × 750-mg tablets) gepotidacin (minimum steady-state urine AUC_{12h} =2256 $\mu\text{g.h/mL}$).

For the global phase III studies (Studies 204989 and 212390), the gepotidacin dose and duration were selected based on in vitro and in vivo studies including experimental animal pyelonephritis studies that simulated human PK exposures of gepotidacin to determine the efficacy of gepotidacin against isolates of *E. coli*, including MDR strains (see the IB for further details). Based on GSK assessment of the limitations of the current acute cystitis efficacy model in rodents, the pyelonephritis model is considered to allow evaluation of antibacterial efficacy in a more robust UTI.

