- **On-therapy (Day 2 to 4) Visit:** Participants will be instructed to return to the study site 1 to 3 days following study treatment administration at Baseline in order to complete the On-therapy Visit. Assessments will be performed as shown in the SoA (Section 1.3), including the following:
 - The On-therapy Visit will be preceded by a documented reminder contact from the study site to the participant 24 ± 4 hours before the scheduled appointment time per the method (e.g., text message, telephone call, e-mail) confirmed with the study site staff prior to departing the study site on Day 1.
 - At the On-therapy Visit should be scheduled to support completion of the predose plasma & spot urine and postdose plasma & pooled urine PK samples collection, if at all possible:
 - Participants will go to the study site before taking the morning dose, have the PK sample collection performed, and then take the morning dose, while aiming to keep the time of dosing as close as possible to 12 hours after the previous evening dose was taken.
 - Participants will remain at the study site until approximately 2 hours (1.5 to 4 hours) after dosing, during which time all Day 1 posttreatment assessments will be performed (i.e., triplicate ECG and postdose PK sample collection), as shown in Section 1.3.
 - At the On-therapy Visit, whenever it is possible, the participant will have the pregnancy test performed at the study site. If the visit coincides with the 8th dose, the participant will take their next dose of study treatment at the study site after negative pregnancy test results are confirmed.
 - Before the On-therapy Visit, if the requirement for the single pregnancy test to be done between dose 4 and dose 8 cannot be done at the study site due to availability of open clinic hours and the investigator considers the participant reliable to accurately perform the study-provided pregnancy test at home will be instructed to do so. If the pregnancy test is negative, those participants will be instructed to take their next dose of study treatment at home via text or by study site staff before going to the study site for their On-therapy Visit.

Note: The On-therapy Visit should be scheduled to support completion of the postdose PK sample collection and ECG within the protocol-defined window. Also, in WOCBP, the high sensitivity pregnancy test must be performed and show negative results at the latest before Dose 8 of study treatment is taken.

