#### 4.3.8.2. Main analytical approach

The analysis is based on the PK population.

All calculations of PK concentrations will be based on actual sampling times that fall within the set PK windows described below.

Summary statistics (n, arithmetic mean, geometric mean, median, standard deviation, minimum, maximum, 95% CI of the arithmetic and geometric means and between participant coefficient of variation [%CV and %CVb]) for plasma and urine gepotidacim concentrations will be provided by the sampling windows in [Table 1](#). If PK concentrations are not quantifiable, these values will be imputed as 0.

PK samples collected outside of the treatment phase will only be listed.

If more than one concentration data is available within the same PK window at a scheduled time point, the data closer to 12 hours post-latest dose will only be used for the summary statistics of Pre-Dose. For Post-Dose, data closer to 2 hours post-latest dose will only be used for the summary statistics.

[figure not shown]
PK concentrations will be listed based on PK (Full) population (i.e. including the participants impacted by GCP violation).

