**Table 1 PK Summary by sampling windows**

Visit	Parameter	PK Window
Baseline Study Day 1	$C_{day1, 0-2h}$	Average concentration post-dose 0 to $\leq 2$ hours
	$C_{day1, >2h}$	Average concentration post-dose $>2$ hours
	$C_{day2-5, pre-dose}$	Average concentration pre-dose
On-Therapy Study Day 2 to 5	$C_{day2-5, 0-2h}$	Average concentration post-dose 0 to $\leq 2$ hours
	$C_{day2-5, >2h}$	Average concentration post-dose $>2$ hours

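### The PK while-on-treatment phase ignores when dosing stopped, and the pre-dose row sets no limit on hours since the last dose, so off-treatment and mistimed samples can enter the concentration summaries

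*SAP*

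**What the plan says.** **Phase.** SAP 4.3.8.1 handles treatment discontinuation by a "while on treatment strategy (treatment phase defined as from first dose to On-therapy Visit"). The PK row of protocol Table 1 (Section 3) uses the same definition. Neither refers to the last dose taken.

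**Inclusion.** SAP 4.3.8.2 states: "All calculations of PK concentrations will be based on actual sampling times that fall within the set PK windows described below". The only stated exclusion by timing is "PK samples collected outside of the treatment phase will only be listed". If two values share a window, the pre-dose summary takes the one nearer to 12 hours after the latest dose.

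**Rows.** In SAP Table 1 the block for "On-Therapy Study Day 2 to 5" has three rows. The pre-dose row reads only "Average concentration pre-dose". The other two are post-dose up to 2 hours, and post-dose beyond 2 hours with no upper limit.

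**Intended sample.** The protocol's Schedule of Activities has the On-therapy plasma sample "collected at pre-dose as trough concentration (i.e., 12 hours post-dose, which is at the end of the dosing interval from the previous dose"). The spot urine sample has the same 12-hour timing.

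**Dosing around the visit.** Protocol 6.1 and 8 have participants arrive before the morning dose, give PK samples and then dose on site, with 12 hours after the evening dose as a target. For participants who do the pregnancy test at home, the same sections say that, after a negative result, "those participants will be instructed to take their next dose of study treatment at home via text or by study site staff" before they travel to the visit.

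**The concern.** A while-on-treatment strategy should stop using data once the participant is no longer on treatment. Here the cut-off is a visit, not the end of dosing. Protocol 7.1 asks participants who stop study treatment to attend all later visits, so a sample can fall after dosing has ended and still lie inside the phase.

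The pre-dose row has a related gap. The protocol gives the sample a pharmacological meaning, 12 hours after the previous dose, and the SAP drops the hours. The tie-break towards 12 hours is not an acceptance window. It acts only when two values compete, and one pre-dose sample per matrix is scheduled.

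At stake is whether the reported pre-dose concentration can be read as the quantity the protocol set out to measure, and whether the stated handling of discontinuation is the one applied.

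**Working it through.** The plan gives no computed figure to reproduce. The check is a reading of the text, followed by an illustration of scale.

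**1. Phase.** Take a participant who stops early and attends the On-therapy Visit 1 to 3 days after the first dose (protocol 8).
- Stopped after dose 1: the sample is 24 to 72 h after the last dose.
- Stopped after dose 2, taken about 12 h after dose 1: 24 − 12 = 12 h to 72 − 12 = 60 h.

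Every such sample lies between first dose and On-therapy Visit, so the exclusion rule does not remove it. SAP 6.2.5 counts time after the last dose date as post-intervention, so most of these samples are on-phase for PK and post-intervention elsewhere in the same SAP. A Day 2 sample after stopping at dose 2 can still be a proper 12-hour sample.

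**2. Row assignment.**

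| Sample at the On-therapy Visit | Row under SAP Table 1 |
|---|---|
| Still dosing, sampled before the on-site dose, 8 h or 16 h after the last dose | Pre-dose; no limit excludes it |
| Took the morning dose at home | Not defined: pre-dose by schedule, or a post-dose row by actual time |
| Stopped treatment, no following dose | Not defined: pre-dose by schedule, or the open-ended row beyond 2 hours |

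In all three cases the sample is summarised somewhere.

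**3. Scale (illustration only).** The documents give no half-life. Assume first-order decline with half-life t of 4 to 16 h. Relative to the 12-hour value, a sample at h hours reads 2^(−(h − 12)/t).

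| Hours since last dose | t = 4 h | t = 9 h | t = 16 h |
|---|---|---|---|
| 8 | 2.00 | 1.36 | 1.19 |
| 16 | 0.50 | 0.73 | 0.84 |
| 48 | 0.002 | 0.06 | 0.21 |
| 72 | <0.0001 | 0.01 | 0.07 |

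Suppose, as a further assumption, that 2% of the samples in a row are at 72 h and the rest at 12 h. With r = 2^(−60/t), the arithmetic mean is multiplied by 0.98 + 0.02r, a fall of about 2%. The geometric mean is multiplied by r^0.02, which is 0.81, 0.91 and 0.95 for t = 4, 9 and 16 h: falls of 19%, 9% and 5%. SAP 4.3.8.2 also sets non-quantifiable values to 0 while planning a geometric mean. One such value makes that mean zero or undefined, and late samples are the likeliest to be non-quantifiable.

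**The case against.** **The SAP does not say these samples are averaged as troughs.** A reader might infer that off-treatment and home-dosed samples certainly enter the trough mean. The documents do not support that. Samples are placed by actual time, and a participant who has stopped has no next dose, so the row beyond 2 hours could take hers. This stands, and it limits the finding to what the text allows. It does not rescue the phase definition, because either row belongs to a summary labelled while on treatment.

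**No steady-state trough is claimed.** A reader might also object that Day 2 samples are pooled with later ones before steady state. The SAP speaks of neither troughs nor steady state here, so pooling limits interpretation but is not an error.

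**The cases may be few.** Protocol 7.1 expects permanent discontinuation to be rare. The home-test route is narrow: the test falls between doses 4 and 8, and protocol 8.2.5 requires it only of women of childbearing potential without 14 days of effective contraception or abstinence. Further sampling detail may be in the Study Reference Manual. All of this stands.

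**Adherence.** The SAP's treatment condition for this estimand disregards adherence. That bears on missed doses while treatment continues. It cannot override the separate strategy named for discontinuation.

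**A firmer size is tempting.** Protocol 4.3 reports that "approximately 460 mg of unchanged gepotidacin was excreted in urine over the steady-state dosing interval of 12 hours", against about 287 mg after a single dose. Read as accumulation, 460/287 = 1.603, so the fraction left at 12 h is 1 − 1/1.603 = 0.376 and the half-life is 12 × ln 2 / ln(1/0.376) = 8.5 h. But the two figures come from different studies and populations, and the single-dose one has no stated collection interval. The minimum urine AUC values in the same section, 2256/807 = 2.80, give about 19 h by the same formula. No half-life should be drawn from these figures.

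**The dose case does not rest on this summary.** The Japanese urine trough that protocol 4.3 compares with MIC comes from a single-dose Phase I study with an 8- to 12-hour window. In this trial, individual exposure will be estimated by a population model of plasma concentrations (protocol 9.3.5).

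**Conclusion.** The point holds on the text. The PK phase, as defined in both documents, keeps samples taken after treatment has stopped, contrary to the named strategy and out of line with SAP 6.2.5. The pre-dose row has no limit on hours since the last dose, so samples well away from 12 hours can be averaged in it. The row for samples after treatment stop or after a home dose is undefined.

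The size cannot be fixed from the documents. Under the assumed half-life of 4 to 16 h, an 8 h sample reads 1.2 to 2.0 times the 12 h value; at 19 h it would read 2^(4/19) = 1.16 times. The share of affected samples is unknown. The consequence is confined to a descriptive summary of a secondary endpoint. The primary consistency analysis does not use these data.

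**What to change.** In SAP 4.3.8 and SAP Table 1:
- Define the On-therapy pre-dose row by actual hours since the last dose, for example 10 to 14 h, and before the on-site dose.
- End the PK treatment phase at the earlier of the On-therapy Visit or one dosing interval after the participant's final dose. For anyone still dosing at the visit, nothing changes.
- Assign samples taken after a home dose to the post-dose rows by actual time, and give the row beyond 2 hours an upper limit so that late samples do not fall into it by default.
- List samples outside these limits without summarising them.
- State how zeros are handled in the geometric mean.

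The protocol passages on dosing at home before the On-therapy Visit and on dosing on site after PK sampling (6.1 and 8) must be reconciled with each other.

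Showing results by study day or number of prior doses is optional.

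The cost is SAP wording and slightly fewer samples summarised. No new data are needed, because protocol 8.4 already records the time of each sample and of the last dose before it.

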#### 4.3.8.2. Main analytical approach

The analysis is based on the PK population.

All calculations of PK concentrations will be based on actual sampling times that fall within the set PK windows described below.

Summary statistics (n, arithmetic mean, geometric mean, median, standard deviation, minimum, maximum, 95% CI of the arithmetic and geometric means and between participant coefficient of variation [%CV and %CVb]) for plasma and urine gepotidacim concentrations will be provided by the sampling windows in [Table 1](#). If PK concentrations are not quantifiable, these values will be imputed as 0.

PK samples collected outside of the treatment phase will only be listed.

If more than one concentration data is available within the same PK window at a scheduled time point, the data closer to 12 hours post-latest dose will only be used for the summary statistics of Pre-Dose. For Post-Dose, data closer to 2 hours post-latest dose will only be used for the summary statistics.

[figure not shown]
PK concentrations will be listed based on PK (Full) population (i.e. including the participants impacted by GCP violation).

**Table 1 PK Summary by sampling windows**

Visit	Parameter	PK Window
Baseline Study Day 1	$C_{day1, 0-2h}$	Average concentration post-dose 0 to $\leq 2$ hours
	$C_{day1, >2h}$	Average concentration post-dose $>2$ hours
	$C_{day2-5, pre-dose}$	Average concentration pre-dose
On-Therapy Study Day 2 to 5	$C_{day2-5, 0-2h}$	Average concentration post-dose 0 to $\leq 2$ hours
	$C_{day2-5, >2h}$	Average concentration post-dose $>2$ hours

#### 4.4. Exploratory Endpoint(s) Analyses

[figure not shown]
CCI

**CONFIDENTIAL**

214144

[figure not shown]
CCI

**CONFIDENTIAL**

214144

[figure not shown]
CCI

**CONFIDENTIAL**

214144

[figure not shown]
CCI

**CONFIDENTIAL**

214144

[figure not shown]
CCI

**CONFIDENTIAL**

214144

[figure not shown]
CCI

**CONFIDENTIAL**

214144

[figure not shown]
CCI

**CONFIDENTIAL**

214144

CCI

CCI

## 4.6. Safety Analyses

The safety analyses will be based on the Safety Analysis population, unless otherwise specified.

### 4.6.1. Extent of Exposure

Exposure will be summarized by treatment group for the Safety population using the following parameters.

- Duration of treatment (days): Rounding of the last dose date/time – the first dose date/time + (0.5 in days) to the nearest integer.
- Average daily dose (mg)
- Cumulative actual dose (mg)
- Compliance rate (%)

In addition, the number of participants with <80%, >=80%-<100% and 100% compliance rate will be summarized. In addition, listing will be produced for the exposure data.

Compliance rate (%) will be calculated as:

Study intervention	Formula
Gepotidacin/gepotidacin placebo	$\frac{\text{total number of tablets taken}}{20} * 100 (\%)$
Nitrofurantoin/nitrofurantoin placebo	$\frac{\text{total number of capsules taken}}{10} * 100 (\%)$

